5. MANAGEMENT OF DATA AND SAMPLES

a. Storage

No samples will be collected or stored. The samples that were previously stored at the Neuroendocrine Core Facility (NCF) have been discarded.

Questionnaires are labeled with a subject number. The master list and computerized data are maintained in password protected computers. Only study personnel will be given a password and have access to the data. Data will be stored without identifiers, and only study personnel with have access to the code key.

Additional information regarding the web site: The servers are located on the main NIH campus, building 10, room 4A11A. The room is locked and accessible only by selected NIMH IRP Computer Support staff. NIMH IRP computer support will collect userID, day/time website is accessed, and the subjects' responses to the questions. The subjects' names will not be used. Two servers will be utilized: one server will be used to host the web application; the second server will be used to store the data. The web application will require userID and password for access. The site itself will be SSL encrypted (https). The MS SQL database that contains the data will be on a separate CNS IRB Protocol Template (rev. 9-21-11)

server, isolating the data should the web server become compromised. The data stored on the MS SQL database will be encrypted and protected. Before deployment to the general public, the ISSO and IRT will perform vulnerabilities scan on the site. All security vulnerabilities will be corrected before the site goes 'live'.

b. Data and sample sharing plan

This protocol is not subject to the Genomic Data Sharing (GDS) Policy. Samples are not collected or stored. Data may be shared with collaborating laboratories at NIH or outside of NIH and/or submitted to NIH-designated repositories and databases if consent for sharing was obtained. Repositories receiving data from this protocol may be open-access or restricted access.

Data will be stripped of identifiers and may be coded ("de-identified") or unlinked from an identifying code ("anonymized"). When coded data is shared, the key to the code will not be provided to collaborators, but will remain at NIH. Data may be shared with investigators and institutions with an FWA or operating under the Declaration of Helsinki (DoH) and reported at the time of continuing review. Sharing with investigators without an FWA or not operating under the DoH will be submitted for prospective IRB approval. Submissions to NIH-sponsored or supported databases and repositories will be reported at the time of Continuing Review. Submission to non-NIH sponsored or supported databases and repositories will be submitted for prospective IRB approval.

Required approvals from the collaborating institution will be obtained and materials will be shipped in accordance with NIH and federal regulations.

Data collected prior to Amendment TT will not be shared.

6. ADDITIONAL CONSIDERATIONS

a. Research with investigational drugs or devices

Acoustic startle and shock device used in this protocol are considered non-significant risk (NSR) devices and will only be used within published guidelines. The auditory startle device is manufactured by Biopac and the shock device is manufactured by Digitimer.

Auditory startle does not meet criteria for a Significant Risk device as outlined Under 21 CFR 812.3(m), as an investigational device that:

1. Is intended as an implant and presents a potential for serious risk to the health, safety, or welfare of a subject

Response: Auditory startle is not an implantable device.

2. Is purported or represented to be for a use in supporting or sustaining human life and presents a potential for serious risk to the health, safety, or welfare of a subject *Response: Auditory startle is not for use in supporting or sustaining human life. It does not present a potential for serious risk to the health, safety, or welfare of participants when used as described in this protocol.*

3. Is for a use of substantial importance in diagnosing, curing, mitigating, or treating disease, or otherwise preventing impairment of human health and presents a potential for serious risk to the health, safety, or welfare of a subject

Response: Auditory startle, as used under this protocol is not of substantial importance in diagnosing, curing, mitigating, or treating disease, or otherwise preventing impairment of human health and does not present a potential for serious risk to the health, safety or welfare of a subject.

4. Otherwise presents a potential for serious risk to the health, safety or welfare of a subject

Response: Auditory startle has been in use numerous for decades and have been cleared by the FDA. Safety guidelines have been developed and updated allowing its dissemination to a wide range of clinical and non-clinical settings. The FDA has generally waived pre-IDE inquiries for auditory startle studies on an NSR device basis. Hence, the CNS IRB, like most US IRBs, has accepted NSR designation for auditory startle within these limitations.

The shock device (electrical stimulator) does not meet criteria for a Significant Risk device as outlined Under 21 CFR 812.3(m), as an investigational device that:

1. Is intended as an implant and presents a potential for serious risk to the health, safety, or welfare of a subject

Response: The shock device is not an implantable device.

2. Is purported or represented to be for a use in supporting or sustaining human life and presents a potential for serious risk to the health, safety, or welfare of a subject *Response: The shock device is not for use in supporting or sustaining human life. It does not present a potential for serious risk to the health, safety, or welfare of participants when used as described in this protocol.*

3. Is for a use of substantial importance in diagnosing, curing, mitigating, or treating disease, or otherwise preventing impairment of human health and presents a potential for serious risk to the health, safety, or welfare of a subject *Response: The shock device, as used under this protocol is not of substantial importance in diagnosing, curing, mitigating, or treating disease, or otherwise preventing impairment of human health and does not present a potential for serious risk to the health, safety or welfare of a subject.*

4. Otherwise presents a potential for serious risk to the health, safety or welfare of a subject

Response: The shock device has been in use numerous for decades and have been cleared by the FDA. Safety guidelines have been developed and updated allowing its dissemination to a wide range of clinical and non-clinical settings. The FDA has generally waived pre-IDE inquiries for shock studies on an NSR device basis. Hence, the CNS IRB, like most US IRBs, has accepted NSR designation for shock device within these limitations.

Study 2f pilots a new method of administering the shock. The shocks are anxiogenic and are usually described as inducing a slightly painful pin-prick sensation (Rhudy et al 2005). Typical experiments include over 20 such stimuli (Rhudy et al 2005). Our shock studies usually include less than 10 shocks and most frequently about 5/6 shocks. Subjects with "cubital tunnel syndrome" do not need to be excluded given than the shocks are not delivered on the arm or wrist.

d. Emotional pictures: The emotional pictures will be selected from a set of standardized stimuli that are frequently used in psychophysiological and brain imaging studies of emotions (Lang, Ohman et al. 1988). Because the intensity of these pictures might make some people uncomfortable, their contents will be fully described to the subjects before participation in the study. In addition, a debriefing will be conducted to assess whether subjects are distressed or negatively affected by the pictures and in need

of psychological supports by a clinician. A clinician will then talk to them and will follow up with a call to see if further supportive contact is needed. If so, then a study clinician will meet with the participant and assess for necessary intervention.

7.2 Assessment of Potential Risks and Benefits

This is a more than minimal risk protocol in healthy volunteers. These experiments may enhance our understanding of how stress and anxiety affect associative learning, that is, the way we learn about our environment. We have minimized risks by delivering electric shosks at a level that is judged by the participant as uncomfortable and tolerable. Subjects may stop the experiment at any time if they find the discomfort to be too great. The risks are reasonable in relation to the anticipated benefit.

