The objective of this pilot study is to learn to implement this new technique. The shock will be administered on the sural nerve in the retromalleolar space and recording of the response from the biceps femoris muscle (see *Electric shock: sural nerve* below). We will learn how to locate the best placement of the stimulating electrodes to stimulate the sural nerve and of the recording electrodes to record the R3 reflex. We will also need to determine the best parameters of stimulation. Finally, we will examine how to organize the equipment in experiments that investigate the interaction between anxiety and cognition. Hence, in a subgroup of subjects, we will pilot delivering sural nerve stimulation while they perform a working memory or vigilance task.

Procedures common to all studies

Startle response

The startle reflex will be elicited with a 102 dB white noise (40-ms duration) delivered binaurally via headphones. The eyeblink component of the startle reflex will be recorded binaurally with two electrodes placed under each eye. Eyeblink responses will be scored in the 20-100 ms window following the onset of the startle stimulus.

Autonomic measures

Heart rate, skin conductance activity (event-related responses and spontaneous fluctuations), and finger pulse volume (FPV) will be recorded during testing to evaluate changes in autonomic arousal. The heart rate will be monitored with two disposable electrodes, one on each wrist. A computer algorithm will detect the R-wave in each cardiac cycle and calculate the number of whole and fractional heart beats for 500 ms periods in each condition. The skin conductance will be measured using two Ag-AgCl electrodes filled with a .05M NaCl electrolyte. Electrodes will be placed on the distal phalanges of the index and second fingers of the left hand. FPV will be measured with a finger plesthymograph.

Grip force measures

The strength of hand compression (i.e. grip force) will be recorded during testing to evaluate behavioral indices of motivation and performance. Participants will hold a hand clench dynamometer which will assess hand compression in units of kilogram-force (kgf). The magnitude of grip force will serve as a within-subject measure of motivation. Additionally, patterns of dynamic grip force behavior will serve as measures of fine motor skill.

Procedures to induce anxiety

Electric shock: forearm or fingers

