Electric shocks are one of the most efficient ways to induce anxiety in the laboratory. The shocks will be delivered through two disk electrodes located on the forearm or on two fingers.

Test shocks

At the beginning of the study a shock workup procedure is conducted to determine the setting for the overall procedure for each subject. The level of shock is initially set at 3.5 μ Amp (the low range). A shock is administered and the subject is asked to rate it on a scale from 1 (not at all painful) to 5 (extremely painful). We then increase the level of shock slightly until the subject identifies the sensation at a rating level of 4. No more than three test shocks are given and the level is selected based on the subjective ratings provided by the participant. No subject will ever receive a shock rated more than 4 for the duration of their study. In addition, subjects are reminded that they have the opportunity to withdraw from the study at anytime if they wish.

Participant rating of the experience:

```
CNS IRB Protocol Template (rev. 9-21-11)
```

At the end of the study subjects are asked to retrospectively rate the shock experiment on a scale from 1 (not at all painful) to 10 (extremely painful). This provides us with an assessment of the overall unpleasantness of the experience during the entire shock experiment.

Electric shock: sural nerve

The shock will be administered on the sural nerve in the retromalleolar space and recording of the response from the biceps femoris muscle. The aim is to have an objective measure of unpleasantness. The R3 reflex will be evoked using a method similar to that described in Rhudy et al (2005). Briefly, electric stimulation of the sural nerve will be four to six rectangular wave pulses of 1- to 2-ms duration every 2 to 5 ms. A trial will begin with 0 mA and increased in 1.0-1.5-mA steps until a R3 reflex is detected. Stimulus intensity will then be decreased in 0.75 mA steps until a reflex is no longer detected. This up–down staircase procedure will be repeated two more times, but with 0.5-mA steps until the R3 threshold is determined. Once the R3 threshold is determined, the intensity of stimulation during experiments in which we used shock to evoke anxiety will be set at 1.2 times the threshold intensity. At this intensity, subjects usually report a slightly painful pin-prick sensation (Rhudy et al 2005).

e. End of Participation

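### Section 7.2 says the participant judges the shock level, but the sural nerve procedure, as far as it can be read, sets it from a reflex with no participant rating

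*Combined protocol and SAP*

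**What the plan says.** Section 7.2 covers the protocol as a whole and exempts no sub-study: "We have minimized risks by delivering electric shosks at a level that is judged by the participant as uncomfortable and tolerable". It then separately gives participants the right to stop, and concludes that the risks are reasonable.

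Section 4(d) describes two ways of setting the level.

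- **Forearm or fingers.** The volunteer rates each test shock from 1 to 5, at most three test shocks are given, and "the level is selected based on the subjective ratings provided by the participant". The same text adds: "No subject will ever receive a shock rated more than 4 for the duration of their study".
- **Sural nerve.** For the search, "A trial will begin with 0 mA and increased in 1.0-1.5-mA steps until a R3 reflex is detected". The current then comes down in 0.75 mA steps until the reflex is lost. The up-down "staircase procedure will be repeated two more times, but with 0.5-mA steps until the R3 threshold is determined". Finally, "the intensity of stimulation during experiments in which we used shock to evoke anxiety will be set at 1.2 times the threshold intensity".

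The Sub-study F text refers to the sural procedure and adds that "in a subgroup of subjects, we will pilot delivering sural nerve stimulation while they perform a working memory or vigilance task". The size of that subgroup is not given. On how the stimulation feels, the Study 2f text in Section 7 cites a published study: "The shocks are anxiogenic and are usually described as inducing a slightly painful pin-prick sensation".

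**The concern.** Section 7.2 names two things that keep the risk acceptable: a level that the volunteer has judged, and the freedom to stop. In the sural procedure as it can be read, the first is replaced by a muscle reflex and a fixed multiplier. A published description of what people usually feel is an expectation. It is not a judgement by the volunteer in the chair.

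This is a more-than-minimal-risk protocol in healthy people who gain nothing directly. If one of the two stated safeguards does not describe what is done in a sub-study, the risk assessment for that sub-study rests on a sentence that does not apply to it. Power and analysis are not affected.

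**Working it through.** The plan gives no figure to reproduce, so the main check sets the texts side by side.

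| Feature | Forearm or fingers | Sural nerve (text that can be read) |
|---|---|---|
| What moves the level up or down | Rating from 1 to 5 | R3 reflex present or absent |
| Level finally used | The one rated 4 | 1.2 times reflex threshold, for anxiety-evoking use |
| Cap | No shock rated above 4 | No rating collected to apply it to |
| Test stimuli | At most 3 | Three up-down passes |

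**Could the forearm rating step also govern the sural search?** Count the fewest stimuli that the written staircase allows, leaving out the 0 mA start.

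1. Passes = 1 + 2 repeats = 3.
2. Each ascent ends on a stimulus that evokes the reflex (at least 1). Each descent ends on one that does not (at least 1). Minimum per pass = 1 + 1 = 2.
3. Minimum per search = 3 x 2 = 6 stimuli, of which 3 x 1 = 3 evoke the reflex.

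This bound needs no assumed threshold, and it can be reached. For illustration, take a threshold of 0.5 mA and a first step of 1.0 mA. The sequence is 1.0 (reflex), 1.0 - 0.75 = 0.25 (none), 0.25 + 0.5 = 0.75 (reflex), 0.25 (none), 0.75 (reflex), 0.25 (none). That is 6 stimuli, 3 with a reflex. A higher threshold needs more steps.

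Six is more than the three test shocks that the forearm work-up permits. The two cannot be the same procedure, and the rating step cannot simply be carried across.

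**Scale.**

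- Volunteers: up to 30 (Section 4(d), Sub-study F; Section 10). Share of the current target: 30/148 = 20.3%.
- If all 30 complete the search: 30 x 6 = 180 stimuli at least, of which 30 x 3 = 90 at least evoke the reflex.
- Task stimulation: no count is possible, because the subgroup size is not stated.

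**Other places where a rating might enter.** The 1-10 rating in Section 4(d) is made at the end of the study and looks back, so it cannot set a level. Section 8 provides camera and intercom monitoring and a way to stop, but no rule for choosing the current.

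**The case against.** The strongest reply is that the available text is incomplete. Part of Section 7 just before the Study 2f risk text is missing from it, and so is the sural consent form. Either could contain a tolerability check or a current limit. This stands. A reader might infer that the plan has no tolerability step or maximum current for sural stimulation anywhere, and the documents do not support that.

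Second, Section 7.2 does not require a numerical rating. A volunteer who lets a stepwise ascent from 0 mA continue, under observation and free to stop, has arguably judged it tolerable. This has some force, but Section 7.2 lists the right to stop as a separate protection. Stopping also comes after the stimulus that was too strong, whereas a rating can hold back the next increase.

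Third, the cap of 4 is worded for every subject, and the nesting of headings is uncertain in text read from PDF. Even if the cap is protocol-wide, the sural steps describe no rating through which to enforce it.

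Fourth, the plan ties the 1.2 multiplier to experiments that use shock to evoke anxiety, while Sub-study F is still looking for the best stimulation parameters. A reader might take it as stated that the F task subgroup receives 1.2 times threshold. That is an inference.

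Fifth, reflex-based setting is deliberate, because the aim is an objective measure of unpleasantness. This is a good reason to keep the reflex as the definition of threshold. It does not prevent a rating from being recorded beside it.

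**Conclusion.** The point holds as a mismatch between a protocol-wide statement and an operative procedure. For Sub-study F, up to 30 volunteers, the procedure as it can be read does not deliver the participant-judged level that Section 7.2 claims. It affects the threshold search and any later task stimulation set from that threshold.

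The counts of at least 6 stimuli per search, and at least 180 if all 30 complete it, describe exposure without a recorded rating. A reader might infer from them that volunteers will receive intolerable or harmful shocks. Nothing in the documents shows that: half of the minimum count does not evoke the reflex, the expected sensation is mild, and participants are watched and can stop.

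The conclusion rests on two assumptions: that the sural paragraph in Section 4(d) is the working procedure for F, and that the missing part of Section 7 adds no rating step. Confidence is therefore moderate. The correction is worth making because it is cheap and concerns safety.

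**What to change.** Keep the R3 reflex as the definition of threshold, and add a tolerability stop on the scale that the protocol already uses.

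- Collect the 1-5 rating after each sural stimulus in the search, and at one test stimulus at the intended task level.
- Stop the ascent at a rating of 4.
- Give no task stimulation above the level rated 4, even where the reflex rule would call for more.
- If 4 is reached without a reflex, record that no threshold was found. There is then no threshold from which to set a task level, so give no task stimulation.

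The cost is one rating per stimulus and one extra test stimulus, within the session of up to 2 hours. Some thresholds may not be obtained, which is acceptable in a pilot meant to learn the technique and is informative in itself. Other sub-studies are unchanged.

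If the sponsor does not want ratings in Sub-study F, limit the Section 7.2 sentence to forearm and finger shocks and justify the sural level separately. This costs one edited sentence and a short paragraph. If the part of Section 7 not available here already contains a sural rating step, repeat it in the Section 4(d) procedure, where the staff running the session will look for it.

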8. SUBJECT SAFETY MONITORING

An Associate Investigator is in an adjacent room to the participant during all phases of the procedures. There is a non-recording camera that allows AI to monitor the subject. The subject is able to wave if there is a problem or simply call out to the AI as the rooms are connected with intercom. Participants are told they may end any procedure at any time by waving to AI or calling out. The AI can end experiments if the subject is unable to follow instructions. The medically responsible physician or members of his/her staff are available by phone or pager for any medical problems that arise.

9. OUTCOME MEASURES

Primary outcome measures: The primary outcome measures will be the startle reflex, and performance on cognitive tasks.

Secondary outcome measures: These measures include psychophysiological measures other than startle (e.g., skin conductance), psychological questionnaires (Spielberger state and trait anxiety), and performance on standard cognitive tests (e.g., working memory capacity).

10. STATISTICAL ANALYSIS

The accrual ceiling for this protocol is 1575 healthy controls. The overall current target N for the protocol is 148 healthy controls.

Sub-study A (previously Study 2a)36 subjectsSub-study C (previously Study 2c)34 subjectsSub-study E (previously Study 2e)48 subjectsSub-study F (previously Study 2f)30 subjects

Study 2a: Working memory and anxiety

Analysis of the data: Startle and performance data will be analyzed with ANOVAs with repeated measures using condition (threat, safe) x Load (low, high). Power analysis: Based on pilot and published works in our lab, we expect an small/moderate effect size for startle potentiation (Cohen's d=0.3). A priori calculations indicate that the testing of 30 participants at an alpha of 0.05 would provide power of 0.80 to detect a significant 2 (Condition) x 2 (Load) interaction on startle response. Assuming a 20% attrition rate, we will collect (about) 36 subjects.

Study 2c: Effect of anxiety on sustained attention to response task (SART)

Analysis of the data: The main analysis is to compare startle magnitude when subjects focus on the task and when their mind wander with ANOVAs with repeated measures using condition (threat, safe) x thought (on task, off task).

Power analysis: Based on pilot works in our lab, we expect an small/moderate effect size for startle potentiation (Cohen's d=0.4). A priori calculations indicate that the testing of 28 participants at an alpha of 0.05 would provide power of 0.80 to detect a significant 2 (Condition) x 2 (Load) interaction on startle response. Assuming a 20% attrition rate, we will collect (about) 34 subjects.

Study 2d: Effect of anxiety on Stroop task

Study is 2d is is closed for accrual. We are currently analyzing the data.

Study 2e: Pilot studies

These pilot experiments are designed to determine the parameter of stimulation of study that will be used in our neuroimaging, psychopharmacological, and clinical studies conducted in our other protocols (03-M-0093, 02-M-0321, 02-M-0263). We use tasks in 4 domains, 1) sensory processing, 2) conflict, 3) executive function, and 4) working memory. We will use 12 subjects per domain for a total of 48 subjects.

Study 2f: Pilot study of sural nerve stimulation

This pilot study investigates the location of the stimulating and recording electrodes and different types of stimulus delivery. We have requested 30 subjects.

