This study will examine whether greater WM capacity or practice is associated with increased or decreased anxiety during performance of a WM task during threat of shock. On the one hand, increase in WM capacity could be associated with more ability to allocate resources to anxious thoughts, therefore increasing anxiety. On the other hand, better WM reflects better ability to screen out intrusive stimuli and thoughts, thereby decreasing anxiety. As for task practice, we hypothesize that practice will make more resources available to allocate to anxious thoughts.

Subjects will be asked to remember verbal and nonverbal stimuli. These stimuli consist of words, pictures, letters or spatial locations in series of stimuli. Participants will be instructed to remember one, two, or three stimuli back from the current stimulus on the screen (n-back task). There will be 2 groups. One group will practice the N-back task

minimally (e.g., 5 min) and the other group will have more extensive training (e.g., 20 min).

Sub-study C: Effect of anxiety on sustained attention to response task (SART)

SART are sustained attention tasks during which a button-press response is made to frequent targets and responses are withheld to rare non targets. SART have been used extensively to study inattention, "off-task thinking", task-unrelated thoughts, and 'mind wandering" (Robertson, Manly et al. 1997). An advantage of this task is that it enables us to identify periods when the mind wanders. When the mind wanders, subjects make errors of commitment (they button-press to non-targets). We will use SART to attempt to identify periods of anxious thoughts.

Subjects will have to respond to frequent targets (e.g., digits 1, 2, 3...) and to withhold response to rare non targets (e.g., 3). We will examine the association between response speed and anxiety as assessed with startle. Mind wandering in SART is associated with faster RT. We will examine whether faster RT is associated with larger potentiated startle. We will also probe subjects' thoughts (on-task, off-task, anxious thoughts) after each startle stimulus to assess whether anxious thoughts predict startle potentiation.

Sub-study D: Effect of anxiety on Stroop task

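### Sub-study A forms two practice groups to examine a practice hypothesis, but its only planned analysis has no practice-group factor

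*Combined protocol and SAP*

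**What the plan says.** Section 4.d, Sub-study A, sets the question: "This study will examine whether greater WM capacity or practice is associated with increased or decreased anxiety during performance of a WM task" carried out under threat of shock. For capacity it leaves the direction open. For practice it commits to one: "we hypothesize that practice will make more resources available to allocate to anxious thoughts". It then builds the design around this: "There will be 2 groups. One group will practice the N-back task" for about 5 minutes, "and the other group will have more extensive training (e.g., 20 min"). It does not state how participants are allocated or in what ratio.

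Section 10, Study 2a, names the model: "Startle and performance data will be analyzed with ANOVAs with repeated measures using condition (threat, safe) x Load (low, high"). The power statement has the same scope, with startle as the outcome: "testing of 30 participants at an alpha of 0.05 would provide power of 0.80 to detect a significant 2 (Condition) x 2 (Load) interaction". The effect size given is d = 0.3 for startle potentiation, and 36 participants are to be recruited in total.

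Section 9 adds no group comparison. It says "The primary outcome measures will be the startle reflex, and performance on cognitive tasks". Among the secondary measures, for the protocol as a whole, it gives "performance on standard cognitive tests (e.g., working memory capacity") as an example.

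**The concern.** Condition and Load both vary within each participant. A model containing only these two factors compares participants with themselves and never compares one practice group with the other. The groups are the one design feature that addresses the practice hypothesis, and the analysis does not use them.

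Two things are at stake. If the plan is followed to the letter, the practice hypothesis goes unanswered although the groups were formed for it. If a group term is added later, at least two candidates exist: Group x Condition and Group x Condition x Load. The choice would then be open after the data are seen, on a primary outcome. If the two tests were independent, taking whichever came out significant would give a false-positive rate of 1 - 0.95 x 0.95 = 0.0975 in place of 0.05.

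**Working it through.** **Inputs from the plan (Section 10, Study 2a):** 30 evaluable participants, 36 recruited, 20% attrition, alpha 0.05, d = 0.3, claimed power 0.80.

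**Assumptions not in the documents:** equal groups unless shown otherwise; two-sided testing, because an F test with one numerator degree of freedom is equivalent to a two-sided t test; effects expressed in SD of the per-subject contrast.

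**1. The plan's own figure.** The 2 x 2 within-subject interaction is a one-sample t test on each participant's difference of differences, with noncentrality d x sqrt(n).
- At d = 0.3 on that scale and n = 30, noncentrality is 0.3 x sqrt(30) = 1.64 on 29 df, and power is 0.355.
- Power of 0.80 at n = 30 needs 0.529 SD.
- Rescaling d as d / sqrt(2(1 - r)) gives 0.53 at r of about 0.84, so 0.80 is reachable with a correlation of that size, but the plan does not state one.

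The stated power therefore does not reproduce from the stated inputs alone. Whichever reading is used, the calculation contains no group term.

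**2. What each model estimates.** For each participant, let D be startle under threat minus startle under safety, averaged over load, and let I be the load difference in that quantity.
- Condition: is the mean of D zero over all participants?
- Condition x Load: is the mean of I zero over all participants?
- Group x Condition: does the mean of D differ between practice groups?
- Group x Condition x Load: does the mean of I differ between practice groups?

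The plan specifies a model containing the first two. The practice hypothesis needs the third or the fourth.

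**3. Precision of the group terms at the planned size.** Each is a two-sample t test on a per-subject score, with standard error sqrt(1/n1 + 1/n2) SD.
- At 15 and 15: sqrt(2/15) = 0.365 SD. For the pooled contrast on 30 participants: sqrt(1/30) = 0.183 SD. The group comparison has twice the standard error.
- 95% confidence half-width at 15 and 15: 2.048 x 0.365 = 0.75 SD.
- Power at 15 and 15, noncentrality d x sqrt(15/2): 0.125 at d = 0.3, 0.262 at d = 0.5, 0.562 at d = 0.8.

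| Completers per group | Difference detectable at 80% power (SD) |
|---|---|
| 14 and 14 | 1.10 |
| 15 and 15 | 1.06 |
| 18 and 18 (no attrition) | 0.96 |
| 10 and 20 | 1.12 |

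The 14 and 14 row is included because 36 x 0.8 = 28.8, slightly fewer than the 30 in the power statement.

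**The case against.** The strongest reply is that Section 10 does not say the groups are pooled, nor that no between-subject factor may be added, and that an analyst would naturally include Group. It is fair that the text omits the comparison and does not exclude it; a reader should not infer that the investigators decided against it. But Section 10 names the factors explicitly here and again for Study 2c. A factor that is not named is not planned, and the choice between the two group terms would remain open.

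A second reply is that Condition x Load is a legitimate aim. Section 2 asks how far cognitive tasks reduce experimental anxiety, and the load interaction bears on that. This stands. A reader might infer that the planned ANOVA is wrong or should be replaced as a target; the documents do not support that. The interaction stays in the enlarged model. Which aim takes priority is for the sponsor to say.

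Third, the hypothesis is directional, so a one-sided test might be argued. The plan specifies ANOVA and gives no sidedness. Even a one-sided contrast at 15 and 15 would need 0.93 SD, so the conclusion would not change.

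One further caution stands. Section 4.d describes one-, two- and three-back, while Section 10 has two load levels, so the three-way term is fully defined only once that mapping is stated.

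**Conclusion.** The omission is established by setting Section 4.d beside Section 10: a stated hypothesis and two groups on one side, and a model without those groups on the other. No other section of the text available supplies the missing term. This conclusion does not depend on any power calculation.

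The size of the consequence does rest on assumptions: group allocation, two-sided testing and the contrast scale. Across the splits shown, only differences of roughly 1 SD of the per-subject contrast are detectable with 80% power.

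Two stronger readings go beyond the documents. A reader might infer that Sub-study A fails its own sample-size target for practice. The plan claims no power for practice and gives no practice effect size; its d = 0.3 is for startle potentiation. A reader might also infer that Condition x Load is securely powered because it is the only test with a power statement. That figure needs about 0.53 SD at n = 30, and d = 0.3 read on the same scale gives about 0.36, so it needs its own check.

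Working-memory capacity, named in the same question in Section 4.d, likewise has no stated analysis. That is a minor point.

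**What to change.** In Section 10, Study 2a, replace the model sentence with wording such as:

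> Startle and performance will each be analysed by a mixed ANOVA with practice Group (minimal, extensive) as a between-subject factor and Condition (threat, safe) and Load (low, high) as within-subject factors. The practice hypothesis is tested by Group x Condition on startle, reported with a 95% confidence interval. The power statement below applies to Condition x Load only; no power is claimed for the practice comparison.

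Group x Condition follows the wording of Section 4.d, which states the hypothesis without reference to load. Section 2 argues that anxious thoughts are limited when working memory is fully occupied, so the sponsor may prefer Group x Condition x Load. Either is acceptable if named before the data are seen. The detectable differences given above depend on an unstated allocation and should not be written into the plan.

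For capacity, state the analysis or say that none is planned.

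The cost is one residual degree of freedom (29 to 28 with 30 completers). No extra participants or procedures are needed, since the groups already exist. The imprecision of the practice comparison becomes visible, and a null result will have to be reported as compatible with small or moderate effects.
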